- **Feasibility and tolerability of the interventions** assessed by enrollment and retention numbers, protocol related adverse events (AE's), and questionnaires assessing satisfaction, quality of life and mood.
- Adherence to interventions assessed both with self-report and with the use of a smartphone application in conjunction with continuous glucose monitoring.

Secondary Outcomes:

- Weight (scale) and body composition (DXA) obtained at baseline (prior to the weight loss intervention), at 12 weeks (following the weight loss intervention), and at a 6mo follow-up time point.
- Physical activity assessed by accelerometry
- Free-living sleep patterns assessed by wrist actigraphy
- Objective (in-laboratory) sleep recording using Compumedics Inc Siesta digital sleep recorders
- Meal timing and energy intake assessed by photographic food records
- Patterns in 24h glucose assessed by continuous glucose monitors over 7 days before and after the weight loss intervention
- Questionnaire based measures of appetite
- HqbA1c and lipids
- Resting metabolic rate and nocturnal energy metabolism by indirect calorimetery

B. Description of Population to be Enrolled:

Inclusion criteria.

- Adult males and females with a BMI of 27-45 kg/m² and weight stable over the previous 6 months;
- Age, 18-50 years old;
- Passing medical and physical screening, and analysis of blood and urine screening samples:
- Typical eating duration >12 hours per day (assessed by questionnaires);
- Own a smartphone
- Reside or work within approximately 30 minutes driving distance of CU-AMC (potential
 participants living outside of this driving distance could be included in the study at the PIs
 discretion).
- For participants in the optional Reproductive Hormone Sub-study: females, age 18-40, with regular menstrual cycles (between 18-40 days).

Exclusion criteria.

- Pregnancy or lactation for women (women who are >6 months postpartum with no plans of becoming pregnant in the next year and who are not currently lactating can be included; oral contraceptives will be allowed if medication has been consistent for the prior 6 months)
- Postmenopausal women (menopausal status will be assessed during the history and physical, with requirement of self-reported regular menstrual cycles for the last year; women who have undergone hysterectomy but with ovaries in place who continue to have regular menstrual symptoms can be included)

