Following completion of the baseline assessments, all participants will receive a 9-month groupbased behavioral weight loss program, with randomized groups meeting separately. Participants will be randomized 1:1 to RCD+TRF or RCD. Groups will be held at the AHWC and will be taught by an RD with experience in leading group-based behavioral weight loss interventions. In case of situations in which in-person classes cannot be held (i.e., due to concern for transmission of disease during the COVID-19 global pandemic), meetings will be held virtually via Zoom. Zoom is a HIPAA compliant web and video conferencing platform. All participants will be provided with a link to join the meeting and instructions regarding optimal conditions in which to join the meeting (i.e., a quiet location with minimal distractions and ability to devote full attention to the meeting). Group meetings will be moved back to in-person when it is deemed safe to do so. Group meetings will take place weekly during weeks 1-12, then monthly between months 4 and 9. Groups will meet separately to maintain intervention integrity. Classes will last ~60 minutes and the curriculum will be delivered using a mix of large group discussion, small breakout discussions, visual demonstrations, and written exercises. The programs will fulfill all recommendations for behavioral interventions outlined in current guidelines³². Current guidelines suggest the most effective behavioral treatment for obesity is a high-intensity, comprehensive weight loss intervention provided in individual or group sessions by a trained interventionist with principle components of a moderately reduced calorie diet, increased PA, and behavioral support to facilitate adherence 32. Curriculum will be based on the Colorado Weigh behavioral weight loss program, which uses a skills-based approach and cognitive behavioral strategies for lifestyle modification with a dietary focus on daily caloric restriction^{57,58}. The Colorado Weigh curriculum includes topics addressing the importance of exercise for weight loss. Specifically, the recommendations are for participants to achieve 150 min/wk of exercise, but exercise will not be supervised. Curriculum for RCD+TRF will be developed by [name], with input from a registered dietitian and will feature similar weekly themes as RCD, but modified to focus on support specific to TRF.

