Dietary and Activity Prescriptions. Both groups will focus on caloric restriction to decrease overall EI. Participants will be given a personalized calorie goal based on their measured RMR. If RMR by indirect calorimetry and by Mifflin St-Jeor equation differ by >10%, then the average of the 2 values will be used. This estimated RMR will be reduced by 10% and then rounded to the nearest 100 kcal

Suggested macronutrient content (55% carbohydrates, 15% protein, 30% fat) will be the same for both groups. Participants in the RCD group will not be given any specific instruction regarding timing of food intake. Participants in the RCD+TRF group will be instructed to eat only during a window of 10 hours, starting within 3 hours of waking. They will also be instructed in specific strategies to support TRF including: strategies to deal with hunger outside eating windows, distraction techniques, and choosing a balanced diet/appropriate portions during feeding windows. All participants will be counseled on the importance of PA for weight loss and will receive a recommendation to perform 150 min/wk of PA.

Self-Reported Dietary Adherence, Effort, and Self-Efficacy: At weeks 4, 8 and 12, participants will be asked to rate on a 1-10 Likert scale: 1) how adherent they were to prescribed study diet over the past week, 2) how hard was it to adhere to prescribed study diet over the past week, and 3) how likely they feel they can adhere to prescribed diet for the next month³⁰. These questionnaires will also be administered monthly from month 4 through 9 to determine whether participants have continued to follow their prescribed dietary pattern. In addition, participants will be asked to use the Meal Logger app (Cohorts 1 and 2) or Google Voice at weeks 4 and 8, and monthly between months 4 and 9 in order to objectively assess adherence to the dietary intervention.

Intervention Safety and Tolerability: Participants will be asked to report AEs to study staff as they occur, to be reported to our IRB as per institutional guidelines. We will collect additional parameters to assess tolerability at week 12 and at the 6 month follow up visit. Quality of life (QOL) will be assessed with the RAND-36^{49,50} physical and mental health component summary score. Mood state will be assessed with the Profile of Mood States 2 (POMS-2)⁵¹⁻⁵³. Eating behaviors will be assessed with the Three Factor Eating Questionnaire (TFEQ)⁵⁴.

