Intervention Acceptability: Satisfaction with both the standard RCD and RCD+TRF program intervention will be assessed at week 12 and month 9 with a questionnaire that asks participants to rate on a 1-10 Likert scale how satisfied they were with specific domains of the intervention. The major domains that will be assessed are satisfaction with: 1) ability to adhere to caloric restriction and time restriction (for RCD+TRF group), 2) content of the dietary support curriculum, 3) content of the exercise support curriculum, 4) group meeting frequency and structure, and 5) weight loss achieved to date. Participants will also be asked in open-ended fashion to provide feedback on each domain of the intervention. We will also assess intervention acceptability by comparing the frequency of protocol related AE's, requirement for protocol modification, and attrition between groups.

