biochemical profile (CBC, Chemistry panel including liver function tests, fasting glucose, TSH) along with blood pressure, heart rate, weight and height will be obtained at baseline. The study physician will contact the family physician, as needed, to clarify any issues that arise. The risk of finding a previously undiagnosed medical condition will be explained clearly as part of the informed consent, with the possibility that the condition(s) might require follow-up evaluation and treatment. This study will be scheduled to minimize time lost from work or studies, and subjects will receive some compensation for the time involved in completing the studies detailed herein.

Members of the Research team including the nursing staff on the CTRC are trained and experienced in all of the methods and measures that will be performed. These measures will be performed in a controlled clinical environment (the CTRC) with access to a full complement of hospital services. As discussed above, patients without significant co-morbidities will be recruited for this study to minimize the risks of serious adverse events.

Extended daily fasting: Participants will be allowed to eat food following the resting metabolic rate test performed at the screening visit. Participants will be encouraged to bring a snack to the visit, but the CTRC can provide a granola bar and juice. Subjects randomized to the TRF+RCD group will be informed of the potential risks and discomforts associated with extended daily fasting prior to starting the behavioral weight loss intervention. Tolerance to the TRF + RCD will be evaluated weekly during the behavioral weight loss program and support will be provided to help subjects manage hunger and cravings.

DXA: The risk of radiation exposure is minimized by having trained technicians administer the procedures, thereby reducing the likelihood of needing repeat assessments. Scans will not be performed in pregnant women. Urine pregnancy tests will be done and verified as negative before DXA scans are done on women of reproductive age.

Continuous glucose monitoring: Subjects will be informed that the CGM sensor may cause from minor skin discomfort and/or skin irritation.

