Venipuncture and blood draws: Subjects will be asked not to donate blood or have blood drawn for any other studies (unless medically necessary) for prior to and following completion of this study to minimize risk of anemia. During venipuncture and catheter placement, standard sterile technique will be utilized and experienced phlebotomists and/or nursing staff will perform venipuncture and sampling catheter placement to minimize bleeding, thrombosis and infection at the puncture site.

Sleep measurement (PSG): Subjects will be informed that measurement of the electrocardiogram (ECG) and electroencephalogram (EEG), electromyogram (EMG), electrooculogram (EOG), nasaloral air thermister and nasal cannula (breathing in and out of the nose & mouth/nasal pressure), respiratory bands placed over the chest and abdomen, may cause some minor discomfort and/or skin irritation due to the paste used to attach the electrodes. Subjects will be informed that the paste used to hold electrodes to the scalp may leave a flaky residue for several days. Aveno cream can be used to help treat skin irritation. Nasal-oral air thermister, nasal cannula and respiratory bands can be adjusted if uncomfortable.

Behavioral weight loss program: We will minimize risks through close monitoring by the study investigators and staff members conducting the weight loss program (weekly contact).

Psychological risks will be minimized by explaining this as being part of the informed consent and making sure that if a significant medical condition is diagnosed as part of the screening, every effort will be made to explain the condition to the subject, with recommendations for follow-up. The stress of physical procedures will be minimized by explaining each procedure as clearly as possible prior to and during the procedure, and having experienced staff perform the invasive procedures.

Data and Safety Monitoring Plan (DSMP)

The safety monitoring will be performed by the research team, with oversight by an independent local Safety Officer. This is an investigator-initiated study being conducted at a single site. The risks in this study are minimized by the use of extensive inclusion and exclusion criteria, and by close monitoring of the research subjects. In addition, the involved researchers are qualified and experienced in all of the study procedures. Nonetheless, since this study places the subjects at

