E. Potential Scientific Problems:

Adherence to the TRF protocol: This will be the first study to our knowledge that will assess the feasibility of using TRF in the context of a reduced calorie diet for weight loss. We will objectively measure compliance to the protocol at baseline and 12 weeks using CGM and photographic time-stamped food logs but will otherwise not know whether subjects randomized to the TRF group were compliant to the protocol. To limit the extent of possible non-compliance to the TRF arm we decided on a shorter intervention for our first study. We are also using a high intensity behavioral support program that will meet weekly to discuss dealing with hunger/cravings or other challenges that might be associated with TRF. We will also ask participants to keep a log documenting daily feeding duration (first and last energy intake events) during all intervention weeks.

F. Data Analysis Plan:

Sample Size Justification:. We will aim to recruit 60 participants in two cohorts.. The sample size was determined for the primary outcome, change in body weight (kg) at 12 weeks. Assuming 20% attrition, we will be left with n=48, or n=24 subjects per group. To justify the sample size, we computed the detectable difference that we have 80% power for based on existing preliminary and published data. We will assume an alpha=0.05 and use two-sample t-tests. We assumed that the RCD group will have similar weight loss as has been shown previously with the standard Colorado Weigh curriculum, in which the mean \pm standard deviation (SD) weight loss using an intent-to-treat analysis at 12 weeks is -4.1 \pm 3.7kg⁵⁷. There are no prior relevant data for 12-week weight loss using TRF in the context of a weight loss intervention. However, prior data from the Gill and Panda study²⁶ of time restricted feeding without a weight loss intervention showed a mean weight loss at 16 weeks of -3.3 kg with a SD=3.4 kg. Given that we are combining the RCD and TRF treatments, the standard deviation is likely to be between 3.4kg and the sum of the variation of the RCD and

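### A weekly tolerance evaluation is named for RCD+TRF only, so the between-arm comparison of protocol-related adverse events may be biased against that arm

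*Combined protocol and SAP*

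**What the plan says.** Four parts of the combined protocol and SAP bear on how AEs and tolerance are collected.

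- **AE collection, both arms** (IV.C, Intervention Safety and Tolerability): "Participants will be asked to report AEs to study staff as they occur". No scheduled AE query is given. The same paragraph schedules quality of life, mood and eating behaviour questionnaires at week 12 and the 6-month follow-up, also in both arms.
- **Weekly tolerance evaluation, one arm** (IV.D, Protection against Risk, Extended daily fasting): "Tolerance to the TRF + RCD will be evaluated weekly during the behavioral weight loss program". The sentence goes on to promise support with hunger and cravings.
- **General monitoring, both arms** (IV.D, Protection against Risk, Behavioral weight loss program): risks are to be limited through "close monitoring by the study investigators and staff members conducting the weight loss program (weekly contact").
- **Contact schedule, both arms** (IV.C, Behavioral Weight Loss Program): "Group meetings will take place weekly during weeks 1-12, then monthly between months 4 and 9". Also: "Groups will meet separately to maintain intervention integrity".

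Two parts use the result. IV.A lists protocol-related AEs as one element of the first primary outcome, feasibility and tolerability, beside enrollment, retention and questionnaires. IV.C, Intervention Acceptability, plans "comparing the frequency of protocol related AE's, requirement for protocol modification, and attrition between groups".

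**The concern.** A fair comparison of AE counts needs the same looking in both arms. Here one arm has a named weekly evaluation of tolerance on top of the common rule, and the other does not. The symptoms that IV.D lists for extended fasting (irritability, nausea, light-headedness) are mild, and people often mention such things only when asked. RCD participants can have them too: IV.D acknowledges adverse effects of dietary change, and both arms reduce calories.

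Other features push the same way. The arms meet separately, and IV.E describes sessions that "meet weekly to discuss dealing with hunger/cravings or other challenges that might be associated with TRF". RCD+TRF participants are told about fasting discomforts before they start. The counted event must be protocol related, and the documents do not say who decides that or that the person is unaware of the arm. A headache-like or nausea-like complaint is easier to tie to the protocol in the arm for which fasting risks are listed.

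At stake is the tolerability evidence on RCD+TRF, the programme this pilot exists to assess and refine. Any distortion from this source would make it look less tolerable than it is.

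**Working it through.** **Step 1. Passages side by side.**

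| Source of AE or tolerance information | RCD+TRF | RCD |
|---|---|---|
| Participant-initiated AE reports | yes | yes |
| Questionnaires at week 12 and 6-month follow-up | yes | yes |
| Weekly staff contact and general monitoring | yes | yes |
| Named weekly tolerance evaluation | yes | not written |
| Rule on whether tolerance findings are recorded as AEs | not written | not applicable |

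The asymmetry is one row. Whether it reaches the AE count depends on the last row, which the plan leaves open.

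**Step 2. Illustration of size.** The plan states no AE rate, AE power or AE test, so there is no figure to reproduce.

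Input from the documents: 60 participants randomized 1:1, so n = 60 / 2 = 30 per arm. Assumed inputs: the same true proportion p with an event in both arms; capture 0.90 in RCD+TRF; capture c in RCD of 0.70, 0.50 or 0.30; every weekly finding enters the AE count.

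Expected participants recorded = n × p × capture. Apparent risk ratio = (p × 0.90) / (p × c) = 0.90 / c, which does not depend on p.

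With p = 0.30, RCD+TRF gives 30 × 0.30 × 0.90 = 8.1. The last column is the exact probability that a two-sided Fisher test at 0.05 rejects although the true risks are equal. Fisher's test is my choice, as the plan names none for AEs.

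| RCD capture c | Recorded in RCD | Apparent risk ratio | False rejection |
|---|---|---|---|
| 0.90 (same as RCD+TRF) | 8.1 | 1.0 | 2.6% |
| 0.70 | 30 × 0.30 × 0.70 = 6.3 | 0.90 / 0.70 = 1.3 | 4.7% |
| 0.50 | 30 × 0.30 × 0.50 = 4.5 | 0.90 / 0.50 = 1.8 | 12.7% |
| 0.30 | 30 × 0.30 × 0.30 = 2.7 | 0.90 / 0.30 = 3.0 | 31.3% |

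For p from 0.20 to 0.60 and c from 0.70 to 0.30, the spurious difference runs from 0.20 × (0.90 − 0.70) = 4 points to 0.60 × (0.90 − 0.30) = 36 points, and false rejection from 2.9% to 77.5%. If weekly findings never enter the AE count, this route adds nothing and the ratio is 1.0.

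**Step 3. The period covered.** The weekly evaluation is promised for the duration of the behavioral weight loss program. IV.C heads that program weeks 1-39 and describes it as 9 months, with weekly meetings in weeks 1-12 only. On that reading, 39 − 12 = 27 weeks have no weekly meeting, and 12 / 39 = 31% do. But the Compensation paragraph ties completion of the program to the 12-week assessments, and the fasting risk in IV.D is described for 12 weeks. On that reading the evaluation and the meetings coincide. The passages do not agree on what the term covers.

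**The case against.** The strongest reply is that the weekly evaluation is a safeguard, not an outcome measure. It sits under risk protection, for a risk stated for that arm only, and is joined to help with hunger and cravings. AE collection is set out elsewhere and is identical in both arms. RCD also has weekly staff contact with close monitoring. An independent Safety Officer reviews all serious AEs and summary reports of all AEs.

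Much of this stands. The contrast is a named evaluation against general monitoring, not active collection against none. The plan does not say that weekly findings become AEs, so bias is possible and not demonstrated. The capture rates above are assumptions, and the range of ratios follows from them. The Safety Officer's review does not remove the difference, because it works on events already recorded.

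Three stronger readings are tempting and not supported.

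- A reader might infer that tolerance in RCD is never evaluated. It is: the questionnaires at week 12 and the 6-month follow-up cover both arms, and both rate the difficulty of adherence at weeks 4, 8 and 12.
- A reader might infer that AE results decide whether a large trial goes ahead. The only numerical criteria, in Sample Size Justification, concern recruitment, retention and timely measurement, and they trigger modification of the intervention.
- A reader might infer that weekly evaluation is impossible in 27 of 39 weeks. That holds only if the program is read as 39 weeks.

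What remains is that staff are told to look for poor tolerance weekly in one arm, with no rule keeping those findings out of a compared AE count or matching them in the other arm.

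**Conclusion.** The concern holds in a limited form. The comparison of protocol-related AEs may be biased against RCD+TRF, because elicitation of mild symptoms is written differently by arm and relatedness is judged without described blinding. It affects one component of one primary outcome; enrollment, retention and the scheduled questionnaires are untouched. The size cannot be derived from the documents. A risk ratio of 1.3 to 3.0 under equal true risk illustrates what could happen. It assumes 90% capture in RCD+TRF, 70% to 30% in RCD, and that weekly findings are counted as AEs. This should be corrected, since the comparison is planned and the remedy is cheap.

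**What to change.** 1. In Intervention Safety and Tolerability and in the extended-fasting paragraph of Protection against Risk, specify one short AE and tolerance checklist for both arms, with the same questions, timing and recording rule. Give it at the existing weekly classes in weeks 1-12 and at the existing monthly contacts in months 4-9. State that its findings are recorded as AEs in both arms.
2. In Primary Outcomes and Intervention Acceptability, compare all AEs by arm regardless of relatedness, with protocol-related AEs as a secondary tabulation.
3. Reconcile the Behavioral Weight Loss Program heading and text, the Compensation paragraph, and the Risks and Protection against Risk paragraphs on whether the program with weekly contact means weeks 1-12 or weeks 1-39.

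The cost is protocol wording and a one-page form at contacts that already take place. More minor AEs will be recorded, mainly in RCD. With equal capture the illustrated ratio returns to 1.0. Participants will still know their arm, so some difference in reporting may remain.

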weeks 12 and 16). The energy content of the diet will be determined based on RMR measured at baseline and reduced by 10% (as per weight loss intervention dietary prescription). In addition, participants in the TRF group will be asked to eat all food within their chosen 10-hour eating window as follows: where their habitual breakfast time is T0, Lunch=+4h, snack=+6h, and dinner=+9.). Participants in the RCD group will eat all meals within the same 12-hour eating window as was followed at baseline. The *rationale* for measuring nocturnal metabolism is that previous studies (including recent studies from our group) show that nocturnal energy expenditure and fat oxidation are independent predictors of longitudinal weight change. It is likely that the RCD+TRF and the standard RCD interventions will have differential effects of nocturnal fuel partitioning which could predict rates of weight regain in the groups.

Polysomnographic (PSG) sleep recording and scoring. During the night spent in the room calorimeter subjects will be fitted with Compumedics Inc Siesta digital sleep recorders. The PSG study will consist of an electrocardiogram (ECG) and electroencephalogram (EEG), electromyogram (EMG), electrooculogram (EOG), and respiratory bands placed over the chest and abdomen. The sleep study will be scored according to revised AASM guidelines. Sleep latencies will be defined as follows: sleep onset latency (SOL), time from lights out to the onset of three continuous epochs of PSG-defined sleep; latency to persistent sleep (LPS), time from lights out to the onset of 10 continuous minutes of PSG-defined sleep; latency to slow wave sleep (SWSL), time from LPS to SWS; and REM sleep latency (REML), time from LPS to REM sleep. Sleep stages (stage 1 sleep, stage 2 sleep, SWS, and REM) will be matched with EE values offset by 2 min to account for the lag-time response of the whole-room calorimeter relative to the timing of the sleep recording.

Behavioral Weight Loss Program (Weeks 1-39).

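### The stated weekly safety monitoring does not match a program that runs to week 39 with monthly meetings after week 12, and adverse events, part of a primary outcome, have no scheduled query

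*Combined protocol and SAP*

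**What the plan says.** All references are to the combined protocol and SAP.

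- **Stated protection.** In Section IV.D, Protection against Risk, the paragraph on extended daily fasting says "Tolerance to the TRF + RCD will be evaluated weekly during the behavioral weight loss program". The paragraph on the behavioral program relies on "close monitoring by the study investigators and staff members conducting the weight loss program (weekly contact"). Neither gives an end week. Section IV.E also says "We are also using a high intensity behavioral support program that will meet weekly", again with no end week.
- **Program as scheduled.** The Section IV.C heading is "Behavioral Weight Loss Program (Weeks 1-39"), and the text under it says "all participants will receive a 9-month groupbased behavioral weight loss program". The schedule is "Group meetings will take place weekly during weeks 1-12, then monthly between months 4 and 9".
- **12-week wording.** The Compensation paragraph ties completion of the program to the week-12 assessments. The Risks paragraph on extended daily fasting gives the 14-hour daily fast a duration of 12 weeks.
- **Adverse events.** Section IV.A lists protocol-related AEs within the primary outcome of feasibility and tolerability. Intervention Safety and Tolerability (IV.C) asks participants to tell staff about AEs when they happen and describes no scheduled query. Intervention Acceptability (IV.C) plans on "comparing the frequency of protocol related AE's, requirement for protocol modification, and attrition between groups" and names no period. Section IV.F adds no AE analysis.

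**The concern.** The protocol classes the study as more than minimal risk, so its account of participant protection should match the contacts that are planned. A reader of Section IV.D would expect weekly follow-up of tolerance for as long as the program runs. Section IV.C does not provide that after week 12.

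There is also a measurement question. Aim 1a concerns a 9-month intervention, and AEs form part of its primary outcome. If AEs are volunteered and no query is scheduled, regular meetings are a natural prompt to mention them. Fewer meetings may mean fewer recorded events with no change in how the diet is tolerated. The weekly tolerance evaluation is named for RCD+TRF alone. If it brings out complaints that are then logged as AEs, that arm has an extra route to recording that RCD does not have.

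**Working it through.** The documents state no total number of contacts, so there is no figure of theirs to reproduce. The check sets the stated frequency against the schedule.

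**Inputs.** Program length is 39 weeks, with weekly meetings in weeks 1-12 and monthly meetings in months 4-9 (all Section IV.C). Assumption: one meeting in each of months 4-9, so 6.

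**39-week reading**

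- Meetings needed for weekly contact: 39.
- Meetings scheduled: 12 + 6 = 18, and 18/39 = 46%.
- Weeks in the weekly phase: 12/39 = 31%.
- Weeks after week 12: 39 − 12 = 27. Of these, 27 − 6 = 21 have no meeting.
- Meeting rate: 12/12 = 1.00 per week, then 6/27 = 0.222 per week. The ratio is 1.00/0.222 = 4.5. By calendar months it is 52/12 = 4.3.

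| Meetings in months 4-9 | Total | Rate per week after week 12 | Fold fall |
|---|---|---|---|
| 5 | 17 | 5/27 = 0.185 | 5.4 |
| 6 | 18 | 6/27 = 0.222 | 4.5 |
| 7 | 19 | 7/27 = 0.259 | 3.9 |

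These figures count group meetings only. Other main-study contacts after week 12 are the post-intervention assessments, the 6-month follow-up visit, and the monthly questionnaires and meal logging. None is weekly.

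**12-week reading**

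- Weekly meetings needed and scheduled: 12 of 12, so the statement is met.
- Weeks with no stated safety contact frequency: 27/39 = 69%.
- The diet does not stop at week 12. Section I gives the intervention a total length of 9 months, and the adherence questionnaires in months 4-9 are there to show whether participants are still following their assigned diet.

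**Which measures depend on contact.** Quality of life, mood and eating behavior are collected at week 12 and at the 6-month follow-up. Satisfaction is rated at week 12 and month 9. These time points are fixed and the same in both arms. That leaves AEs, and any record kept of the weekly tolerance evaluation, as the elements exposed to meeting frequency.

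**A constant interval is already available.** The adherence questionnaires are given at weeks 4, 8 and 12 and then monthly in months 4-9, which is 3 + 6 = 9 occasions. Spacing is 12/3 = 4 weeks in the first phase and 27/6 = 4.5 weeks in the second, so an item placed there would have a nearly equal recall interval throughout.

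**The case against.** The strongest reply is that the weekly statement was written for the first phase. It answers the extended-fasting risk, which Section IV.D itself describes as lasting 12 weeks, and several passages treat the weight loss intervention as complete at week 12. On that reading weekly evaluation is fully delivered. This stands as a plausible reading. It does not settle the matter, because the Section IV.C heading and text define the program as 39 weeks, and the 12-week reading leaves the later phase without a stated frequency.

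Follow-up also does not stop at week 12. AE reporting has no end date, participants rate monthly how hard the diet is to follow, and tolerability and satisfaction are measured again at the end. This stands too. The gap is a stated safety contact frequency, not all follow-up.

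Three stronger inferences are tempting, and the documents do not support them:

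- *The later phase will look better tolerated than it is.* No AE query at meetings is described, so a ratio of meeting rates is not a ratio of detection rates. No early-versus-late AE comparison is planned either.
- *The whole 9-month tolerability result mixes two levels of ascertainment.* Only AEs and any weekly tolerance record could be affected. The plan also does not say that AEs will be pooled over 9 months; it is silent on period.
- *The drop in meetings biases the comparison between arms.* Both arms follow the same schedule, so the drop alone does not. Any difference by arm would have to come from the tolerance evaluation being named for RCD+TRF only, and that wording may simply reflect its place under a risk specific to that arm.

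**Conclusion.** The inconsistency is real and holds on either reading. Either the schedule supplies 18 of 39 weekly contacts, or 27 of 39 weeks have no stated safety contact frequency while the diet continues. The meeting rate falls about four-fold after week 12 (4.3 to 4.5 with one meeting per month; 3.9 to 5.4 if 7 or 5 are held).

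The statistical consequence is limited and conditional. AE capture may be less sensitive after week 12 and may differ by arm. The size of either effect cannot be estimated from the documents. It depends on how far meetings prompt reporting, and on whether findings from the weekly tolerance evaluation are recorded as AEs. Quality of life, mood, eating behavior and satisfaction are not affected. The point is worth correcting because the correction is cheap and AEs belong to a primary outcome; it does not undermine the trial.

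**What to change.** 1. Reconcile the program schedule in Section IV.C, the Compensation paragraph, and the Risks and Protection against Risk paragraphs in Section IV.D. Use one definition of the program, and state monitoring that matches the contacts held in each phase. Which frequency is right is for the investigators to decide.
2. Add one fixed AE/symptom item to the adherence questionnaires at weeks 4, 8 and 12 and monthly in months 4-9, with recall since the last questionnaire and identical wording in both arms.
3. Tabulate AEs by arm for weeks 1-12 and weeks 13-39, and state that a fall after week 12 will not be read as improved tolerance.

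The cost is some protocol wording, one questionnaire item and one extra split in the AE table. Counts per phase will be smaller and less precise, which matters in a study of 60. If data collection has ended, steps 1 and 3 remain possible, assuming AE dates were recorded.
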